6.2. Adjustments for Covariates

Stratification factors of this study include HbA1c stratum ($\leq 7.0\%$, $> 7.0\%$) and percentage of time with SG values from 70 to 180 mg/dL over the 2 weeks prior to randomization ($\leq 75\%$, $> 75\%$). Stratification factors will be entered into the IWRS for randomization and also collected in the database by Carelink raw data or central laboratory. The analysis models will use the stratification factors as collected in the database (e.g HbA1c stratum according to the central lab at baseline and percentage of time with SG values from 70 to 180 mg/dL over the 2 weeks prior to randomization calculated from the CareLink raw data).

Other analyses will include the stratification factors as noted in Sections 6.9 to 6.10.

6.3. Handling of Dropouts or Missing Data

For continuous variables, missing data will be addressed by using a MMRM analysis for continuous longitudinal variables. The MMRM model provides consistent estimator when data is missing at random. The model implicitly adjusts for missing data through a variance-covariance structure.

6.4. Multiple Comparisons/Multiplicity

Treatment comparisons will be performed for the primary objective (Section 6.9.1) at the full significance level of 0.1. No multiplicity adjustments will be made for secondary and exploratory objectives.

6.5. Patient Disposition

Patient disposition will be displayed in a flowchart showing the number of patients entered, enrolled, randomized, and discontinued across the lead-in period, Period I, and Period II.

Frequency counts and percentages of the Randomized Population completing and discontinuing from the study will be presented for overall and by each treatment sequence and period. Reasons for discontinuation from the study will be summarized for overall and by treatment sequence and period. Reasons for discontinuation from the study at Visit 801 will be summarized by treatment sequences.

Frequency counts and percentages of all patients entered, enrolled, and discontinued from the study during the lead-in period will be summarized. Reasons for discontinuation during screening will be summarized for the Entered Population. Reasons for discontinuation from the study and from the treatment during the lead-in period will be summarized for the Enrolled Population.

A listing of the primary reason for study/treatment discontinuation will be generated for the Enrolled Population.

A listing will be generated for the Randomized Population, including the following variables but not limited to: investigator ID, patient ID, date of signature of informed consent form, treatment sequence assignment, randomization date, first and last dose date in each treatment period (lead-in, Period I, and Period II).

6.6. Patient Characteristics

A summary table for overall and by treatment sequence will be generated for patient characteristics at study entry using the Randomized Population. The following variables will be included but not limited to: age, age groups (<40 and \geq 40 years, and <65, \geq 65 to <75, \geq 75 to <85, \geq 85 years), sex, country, ethnicity, race, height, weight, body mass index (BMI), BMI groups (<25, \geq 25 to <30, \geq 30 to <35, and \geq 35 kg/m²). No statistical comparisons between treatment sequences will be performed. For continuous variables, the following statistics will be provided: mean, SD, minimum, maximum, and median. For categorical variables, summary statistics will include sample size, frequency, and percentage. A listing of patient characteristics at baseline will be provided.

A similar summary of diabetes characteristics will also be generated. The following variables will be included but not limited to: duration of diabetes, duration of CSII use, duration of 670G use, infusion set cannula length (6 mm or 9 mm), the type of rapid-insulin at study entry, the pump speed at study entry and baseline, total daily dose at study entry, percentage of time with SG values from 70 to 180 mg/dL over the 2 weeks prior to randomization at study entry, HbA1c at study entry and baseline, and HbA1c stratum at baseline.

A listing of patients whose stratification factor value entered into the IWRS (for treatment assignment) is different from the clinical database will also be provided.

The total daily insulin dose for the last 3 days prior to screening will be entered into the eCRF. The dose at study entry will be calculated as the mean of the doses for the last 3 days prior to the visit. Doses will be summarized in U and U/kg. Total daily insulin dose will also be presented by the definitions in protocol exclusion criterion #19 (\leq 100 U, >100 U).

For the Randomized Population, the number and percentage of patients with historical conditions will be summarized using Medical Dictionary for Regulatory Activities (MedDRA) Preferred Term (PT) (without regard to System Organ Class [SOC]), and the number and percentage of patients with preexisting conditions will also be summarized using MedDRA PT (without regard to SOC). Historical conditions are conditions that end prior to informed consent and preexisting conditions are conditions that are still ongoing at informed consent. Events will be ordered by decreasing frequency.

All baseline measures will be summarized for overall and by treatment sequence. No statistical comparison between treatment sequences will be performed given the small sample size of this study.

6.7. Treatment Compliance

No analysis for treatment compliance is planned for this study.

6.8. Concomitant Therapy

Concomitant medications will be summarized and compared between treatments using Prescott's exact test for the Randomized Population during the 2 randomized treatment periods (Period I and Period II). The percentages of patients receiving each concomitant medication will be summarized by treatment using PT nested within Anatomical Therapeutic Chemical (ATC) Level 3 code. Medications will be ordered by decreasing frequency within ATC level. Concomitant medication used during the lead-in period will also be summarized for the Enrolled Population.

6.9. Efficacy Analyses

6.9.1. Primary Outcome and Methodology

The primary objective of this study is to compare LY900014 and Humalog with respect to the percentage of time with SG values within range (70 to 180 mg/dL, both inclusive), during the last 2 weeks of each 4-week treatment period. The analysis model (MMRM) and selection of covariance structure are described in Section 6.1.

The primary analyses will be tested at the full significance level of 0.10, using data collected from the Randomized Population, while patients are on IP (ie, from first dose to last dose) and on pump.

Derivation and analysis of primary endpoint (derived for 24-hour, daytime and nighttime and by-meal) and other CGM endpoints are described in Section 6.13.

6.9.2. Other Secondary Efficacy Analyses

The analyses described in Section 6.9.2 will include data collected from the Randomized Population. Details for the CGM analyses are described in Section 6.13.

For the following secondary efficacy endpoints during the last 2 weeks of each 4-week treatment period, an MMRM model similar to that for the primary endpoint will be used:

- actual and change from baseline in insulin doses, including mean total daily basal (U/day, U/kg/day), mean total daily bolus (U/day, U/kg/day), and mean total daily insulin dose (U/day, U/kg/day) and mean total daily bolus /mean total daily insulin dose ratios (%)
- actual and change from baseline in percentage of time (per week) spent in Auto Mode, during the last 2 weeks of each 4-week treatment period
- actual and change from baseline in percentage of time with sensor glucose values <54 mg/dL as measured by CGM

In addition, the longitudinal observations of actual and change during each 4-week treatment period in HbA1c and 1,5-AG will be summarized by period and by treatment sequence. No treatment comparison will be conducted.

To assess the insulin doses over the course of 3 days of continuous infusion, the mean total daily basal and mean total bolus doses during the last 2 weeks of the lead-in and each 4-week treatment period, will be derived based upon the CareLink raw data collected on Day 1, Day 2, and Day 3 of infusion set wear and summarized by treatment. The insulin doses will also be summarized by infusion set wear day, and by both infusion set wear day and meal (0 to 4 hours after the start of meals, excluding data collected after the next meal for the current meal). Only data from the infusion sets with ≥ 60 hours of wear will be included in these doses analyses by infusion set wear day. The treatment comparison will be conducted using an MMRM model similar to that for the primary endpoint.

Before the database lock, it was identified that 1 patient had to replace the pump in the middle of the study and Auto Mode was unavailable for at least 48 hours, and thus data from this patient will be excluded from analysis of percentage of time (per week) spent in Auto Mode.

6.9.3. Exploratory Efficacy Analyses

An MMRM model similar to that for the primary endpoint will be used to analyze actual and change from baseline in pump factors that affect insulin dosing.

The initial settings for pump factors, including carb ratio (CR), active insulin time (AIT), and insulin sensitivity factor (ISF), will be captured in eCRF at Visit 2, Visit 4 and Visit 7 for the lead-in, Period I and Period II, respectively. Any changes during any treatment period will be captured in the CareLink raw data and associated to meals for CR and ISF. A listing of pump factors will be provided, including data collected at Visit 2 and changes captured in the CareLink raw data.

Actual and change from baseline in pump factors, including CR by meal, ISF by meal and AIT, will be summarized and compared between LY900014 and Humalog using an MMRM models as specified in Section 6.1. Only postbaseline measures at Visit 7 and Visit 10 will be included for analyses.

In addition, CGM outcomes that are not included in the primary and secondary efficacy endpoints will be analyzed as exploratory efficacy endpoints. Details for the CGM analyses can be found in Section 6.13.

6.10. Safety Analyses

6.10.1. Extent of Exposure

Duration of exposure to study drug will be summarized based upon CRF data. The following summary statistics will be provided: n, mean, SD, median, minimum, maximum, and sum (that is, total patient-years of exposure). The number and proportion of patients falling into the following different exposure categories will also be summarized: <7 days (>0 and <7 days), ≥ 7 and <14 days, ≥ 14 and <28 days, and ≥ 28 days.

Patients who complete the study treatment period are required to complete a safety follow-up visit without study drug; and patients who discontinue the IP unplanned are required to discontinue from the study (ITSM Protocol 8.1 to 8.2).

6.10.2. Adverse Events

Events that are newly reported after the first dose of rapid-acting insulin provided as study drug (ie, open-label Humalog used during the lead-in period or IP used during each of the two 4-week randomized treatment periods) or are reported to worsen in severity from baseline (defined in [Table ITSM.6.2](#) for each specific study period) will be considered treatment-emergent adverse events (TEAEs). Events that continue during more than 1 study period (lead-in, Period I, Period II) with the same severity will only be counted once for the first study period.

The MedDRA Lowest Level Term (LLT) will be used in the treatment-emergent assessment. The maximum severity for each LLT during the baseline period will be used as baseline severity. For events occurring on the day of first dose of blinded insulin provided in this study during each treatment period (lead-in, Period I and Period II), the CRF-collected flag will be used to determine whether the event started or worsened post-treatment, and/or the treatment of which period the AE should be assigned.

In an overview table, the number and percentage of patients who experienced a TEAE, experienced a serious adverse event (SAE), died due to an AE, and discontinued from study due to an AE will be summarized.

The number and percentage of patients with SAEs and who discontinued from the study due to an AE will be summarized using MedDRA PT nested within SOC if any such events occurred. Prescott's exact test will be performed for treatment comparison. The number and percentage of patients with TEAEs will be summarized by treatment using MedDRA PT nested within SOC. Events will be ordered by decreasing frequency within SOC. As an additional table, the percentages of patients with TEAEs will be summarized by treatment using MedDRA PT (without regard to SOC). Events will be ordered by decreasing frequency in total group. Statistical comparisons will be applied at both the SOC and PT levels. Prescott's exact test will be performed for treatment comparison.

The number and percentage of patients with TEAEs by maximum severity will be summarized by treatment using MedDRA PT nested within SOC. For each patient and TEAE on each treatment, the maximum severity for the MedDRA PT is the maximum postbaseline severity

observed from all associated LLTs mapping to the MedDRA PT during the corresponding randomized treatment period for the specified treatment. No statistical comparison between treatments will be conducted.

The number and percentage of patients who experienced a SAE including deaths and SAEs temporally associated or preceding deaths will be summarized by treatment using MedDRA PT (without regard to SOC). Events will be ordered by decreasing frequency within SOC. A listing of all SAEs (including data collected during the safety follow-up period) will also be provided.

The number and percentage of patients who discontinued from study in Period I and Period II due to an AE will be summarized by treatment using MedDRA PT (without regard to SOC). Events will be ordered by decreasing frequency. A listing of all AEs as reason for study discontinuation will also be provided.

For events that are gender-specific (as defined by MedDRA), the denominator and computation of the percentage will include only patients from the given gender.

Table ITSM.6.3 summarizes the planned analyses and the requirement of analysis data for different analysis periods.

Table ITSM.6.3. Adverse Event Analysis Periods

Analysis Period	Analysis Population	Analysis	IP USE	Treatment
Lead-in Period	Enrolled Population	AE overview; TEAE by PT; SAE, discontinuation due to AE	N/A	Open-label Humalog
Treatment Period (0-8 Weeks)	Randomized Population	AE overview; TEAE by PT nested within SOC and by PT; TEAEs by maximum severity; SAE; discontinuation due to AE; other notable AEs	All data regardless of IP use	LY900014, Humalog
Safety Follow-up Period	All patients in the Randomized Population who enter follow-up period	TEAE by PT	All data	Overall ^a

Abbreviations: AE = adverse event; IP = investigational product; N/A = not applicable/available; PT = preferred term; SAE = serious adverse event; SOC = system organ class; TEAE = treatment-emergent adverse event.

^a overall means that data will be summarized in total and no by-treatment summary or statistical analysis will be included.

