10.3.4. Safety Analyses

Safety measures will include AEs, hypoglycemia, vital signs, treatment exposure, and laboratory measures.

Events that are newly reported after the first dose of rapid-acting insulin provided as study drug (i.e., open-label Humalog used during the lead-in period or IP used during each of the two 4-week randomized treatment periods) or reported to worsen in severity from baseline (details will be described in SAP) will be considered -TEAEs. Events that continue during more than 1 study period (lead-in, Period I, and Period II) with the same severity will only be counted once for the first study period.

Serious AEs, AEs reported as reason for discontinuation from the IP or study, and TEAEs will be summarized in tables using the Medical Dictionary for Regulatory Activities (MedDRA) PT, sorted by decreasing frequency within the LY900014 treated-patients. Treatment-emergent AEs

will also be summarized by PT sorted by decreasing frequency within SOC for all TEAEs and by maximum severity. For events that are gender-specific (as defined by MedDRA), the denominator and computation of the percentage will include only patients from the given gender. The number and proportion of patients with at least 1 event for each type of event will be summarized and compared between treatments using Prescott's exact test.

Hypoglycemia rates will be summarized for periods of 1 year, and 100 years (severe hypoglycemia only) for both treatment periods. Wilcoxon Signed-Rank test and Prescott's exact test will be used instead to analyze the rate and incidence of hypoglycemia events, respectively.

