Pump factors - CR, ISF, and AIT ^b	All patients in the Randomized Population with a baseline and at least one post-baseline observation	Last value of Visits 2-4 prior to or on the date of the first dose of IP	Last observation 1 day prior to Visit 7 and last observation 1 day prior to Visit 10 prior to last dose in IP of each randomized treatment period (Period I and Period II) excluding data (if any) that are collected while patients temporarily are off pump or off IP

Baseline and Post-Baseline Definitions and Patient Population by Study Period and Type of Analysis

Study Period/Analysis	Patient Population	Baseline Observations	Post-Baseline Observations
4-Week of Each Randomized Treatment Period Regardless of IP use (from randomization to Week 4 of each randomized treatment period regardless of IP use)			
TEAEs	Randomized Population	Prior to first dose of randomized IP (or Visit 4 if the dose date is missing)	Each 4-week randomized treatment period regardless of IP use
Weight and vital signs	All patients in the Randomized Population with a baseline and a post-baseline observation	Last of Visits 2-4	Visits 7 and 10 regardless of IP use
Week 2-4 of Each Randomized Treatment Period while on IP			
CGM outcome variables	All patients in the Randomized Population (with a baseline and a post-baseline observation for continuous variables, unless otherwise specified ^c)	From first to last dose of open-label Humalog, excluding data (if any) that are collected while patients temporarily are off pump or off open-label Humalog	From first to last dose of IP in each randomized treatment period (Period I and Period II), excluding data (if any) that are collected while patients temporarily are off pump or off IP
Week 2-4 of Each Randomized Treatment Period Regardless of IP			
Basal, bolus, and total insulin doses, bolus/total insulin dose ratios ^d	All patients in the Randomized Population with a baseline and a post-baseline observation	Last of Visits 2-4	Visits 7 and 10 regardless of IP use
Basal, bolus, and total insulin doses, bolus/total insulin dose ratios by infusion set wear day, by meal, and by infusion set wear day and meal ^e	All patients in the Randomized Population with a baseline and a post-baseline observation	Last of Visits 2-4	Last observed value before/at Visit 7 and before/at Visit 10 regardless of IP use

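### Read literally, the SAP counts an adverse event that began in Period I and continues at lower severity in Period II as treatment-emergent on both insulins

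*SAP*

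**What the plan says.** SAP 6.10.2 gives two routes to a TEAE. The first is for "Events that are newly reported after the first dose of rapid-acting insulin provided as study drug", which covers open-label Humalog in the lead-in and the blinded product in either period. The second is for events that "are reported to worsen in severity from baseline", with baseline taken from Table ITSM.6.2. The assessment is made at LLT level, and "The maximum severity for each LLT during the baseline period will be used as baseline severity".

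Table ITSM.6.2 (SAP 6.1) has one TEAE row for the two randomized periods. Its baseline is "Prior to first dose of randomized IP (or Visit 4 if the dose date is missing"; the Visit 4 fallback places this at the start of Period I. Its post-baseline window is "Each 4-week randomized treatment period regardless of IP use". No separate baseline at Visit 7 is given for Period II.

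The only protection against counting one event twice is the once-only sentence: "Events that continue during more than 1 study period (lead-in, Period I, Period II) with the same severity will only be counted once". Protocol 10.3.4 carries the same limit: "with the same severity will only be counted once for the first study period". Neither document says how to count an event that continues at lower severity.

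**The concern.** Patients go straight from one insulin to the other at Visit 7. Protocol 5.4 relies on the last 2 weeks of each period to limit carryover, but SAP 6.1 analyses adverse events over the whole 4 weeks, so that buffer does not protect them.

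Take an infusion site reaction that was absent before randomization, moderate on the Period I insulin and still resolving as mild after Visit 7. In Period II it is above its stated baseline. Its severity differs from Period I, so the once-only sentence does not remove it. It would be attributed to the second insulin although it began on the first and is getting better.

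TEAEs are compared between insulins with Prescott's exact test at system organ class and preferred term level (SAP 6.10.2). Systemic hypersensitivity and infusion site reactions are drawn from the same TEAE set (SAP 6.10.4.2 and 6.10.4.3). An event on one insulin that is also charged to the other raises the second insulin's incidence and removes a discordant patient from the test.

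**Working it through.** The plan states no figure to reproduce here, so the check has two parts.

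**1. Apply the rules to every lower-severity pattern**

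Literal rule: an event counts in a period if its severity there exceeds the pre-randomization maximum for that LLT. Period II is dropped only if its severity equals that of Period I. Proposed rule: a continuing event counts in Period II only if its severity exceeds the larger of its baseline and its Period I maximum. Three severity steps allow three improving patterns: moderate to mild, severe to mild, and severe to moderate.

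| Severity before randomized product | Patterns counted on the second insulin, literal rule | Proposed rule |
|---|---|---|
| Absent | 3 of 3 | 0 of 3 |
| Mild | 1 of 3 (severe to moderate) | 0 of 3 |
| Moderate | 0 of 3 | 0 of 3 |
| Severe | 0 of 3 | 0 of 3 |

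The problem is therefore confined to LLTs absent before randomized product, or still above their earlier maximum in Period II. Events carried over from the lead-in are not affected, because the lead-in lies inside the baseline.

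**2. Effect on Prescott's test**

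The 21 patients per sequence come from Protocol 10.1. All event counts are assumed, since the documents give no adverse event or carry-over rates. Each patient scores +1 for an event in Period I only, −1 for Period II only, and 0 otherwise. The scores are permuted between sequences, two-sided. Sequence A takes LY900014 first and Sequence B takes Humalog first.

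*Example 1: events on LY900014 only.* Four Sequence A patients score +1 and two Sequence B patients score −1. This is the most extreme allocation, and the two tails are equal:

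- No carry-over: p = 2 × C(36,17)/C(42,21) = 0.032.
- One of the four Sequence A events carries over and becomes a tie: p = 2 × C(37,18)/C(42,21) = 0.066.
- Two carry over: p = 2 × C(38,19)/C(42,21) = 0.131, above the 0.10 level.

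Patients with the event on Humalog go from 0 to 1 or 2 of 42.

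*Example 2: events on both insulins.* Sequence A has four LY900014-only events in Period I. Sequence B has two LY900014-only events in Period II and two Humalog-only events in Period I.

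- No carry-over: six scores of +1 (four in A, two in B) and two of −1 (both in B) give p = 0.283. Patients with events are 6 on LY900014 and 2 on Humalog.
- Both Humalog events carry over onto LY900014: those two patients become ties. The scores are then those of Example 1 without carry-over, so p = 0.032. LY900014 rises to 8 patients and Humalog stays at 2.

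**The case against.** The strongest reply is that the double count is stated nowhere. An improving event that began in Period I is not newly reported in Period II and is not worse than it was. The TEAE definition in Protocol Appendix 1 requires an event to arise in a given treatment period or to be worse than before treatment. The first-dose-day rule in SAP 6.10.2 looks for events that began or got worse. A programmer working event by event could fairly leave the improving event in Period I only.

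That reading is not excluded, so a reader should not infer that the SAP expressly assigns such events to the second insulin. But the Appendix 1 definition does not say which period's start is the reference, and the first-dose-day rule covers only events on that day. The once-only sentence also has real work to do only if continuing events can qualify again: for lead-in events the baseline already does the job, so it bites only between Period I and Period II. With both readings open, attribution by treatment is left to whoever writes the program.

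A reader might also infer that the error always pulls toward no difference. Example 2 shows otherwise; the direction depends on which insulin the affected events began on.

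Two further points stand. The counts are hypothetical, and in Example 1 one carry-over leaves p below 0.10. The stakes are limited too: adverse events fall under Objective 8, listed as tertiary/exploratory, and these tests have no multiplicity adjustment.

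The last objection is to the remedy. An event severe in Period I, mild by crossover and moderate in Period II worsened on the second insulin, yet would not count there. This is a small cost. It follows the SAP's own convention of taking the maximum severity as baseline, and it should be stated openly.

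**Conclusion.** The concern holds as a defect in the counting rule on its literal reading. With one pre-randomization baseline and a same-severity exemption, an improving event whose LLT was absent before randomized product counts on both insulins in all three lower-severity patterns. Where the LLT was mild before randomization, one pattern of three is affected; where it was moderate or severe, none is.

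The effect is a misattributed event, a higher incidence on the second insulin and one fewer discordant patient per case. The shifts from 0.032 to 0.131 and from 0.283 to 0.032 show that a few patients can move a comparison across 0.10 in either direction. They rest on assumed counts and on the lower severity being recorded in Period II, and they do not predict this trial's results.

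A reader might infer that all continuing events are double counted or that the efficacy conclusions are at risk. The documents support neither: unchanged severity is exempt, and the primary and secondary endpoints do not use the TEAE rule.

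**What to change.** In SAP 6.10.2 and Protocol 10.3.4, change *with the same severity* to *with the same or lower severity* in the once-only sentence. Add that an event continuing from Period I counts in Period II only if its severity exceeds its Period I maximum, in line with the SAP's maximum-severity baseline rule. New onsets in Period II count as now.

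State the downside alongside: an event that eased before crossover and then worsened in Period II, without passing its Period I maximum, is not counted in Period II. A listing of such events would keep them visible.

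The cost is a short text change in two places, one programming condition and, if wanted, one listing. No new data are needed.
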